6.0 PRE-TREATMENT EVALUATION
 (See Appendix I)

	Investigations/Activity	Timing
Diagnostic Procedure	
 • LEEP, cone or biopsy¹ 	Prior to randomization
History and Physical Exam including	
 • recto-vaginal examination with speculum or colposcopy² • medical, surgical and obstetrical history • co-morbidities • performance status • height and weight • tobacco smoking history 	After diagnostic procedure and within 12 weeks of randomization
Other Investigations	
 • pregnancy test³ 	Prior to randomization
Adverse Events ⁴	
 • baseline adverse events evaluation 	Within 14 days prior to randomization
Radiology	
 • chest x-ray or chest CT scan • pelvic MRI⁵ – see Section 5.1.5 for specific requirements of MRI 	After diagnostic procedure and prior to randomization
Patient Reported Outcomes	
 • Quality of Life questionnaire (composed of the QLQ-C30, QLQ-CX24) • Sexual Health questionnaire (composed of the FSDS-R and the FSFI)⁶ • Health Economics questionnaire (composed of the HUI3 and EQ-5D)⁷ 	Within 6 weeks prior to randomization.

 1. The initial diagnostic specimen must be reviewed by the Local Reference Pathologist (LRP) per the criteria outlined in the Surgery/Pathology manual (see LEEP/cone/biopsy checklist). 2. A recto-vaginal examination is preferred but not mandatory. A bimanual exam is also acceptable. 3. A pregnancy test is only required for women of childbearing potential. This test can be a serum test or a urine test. 4. Adverse events will be recorded and graded according to the NCI Common Terminology Criteria for Adverse Events (CTCAE), Version 4.0 (Appendix V). 5. Pelvic MRI is not required for patients with stage IA2 disease who underwent a LEEP or cone. 6. For patients who consented to this optional study component. 7. Mandatory for English and French speaking patients from Canada, the UK and France. 		

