- A. The patient leaves the clinic before the questionnaire could be administered, or someone forgets to give the questionnaire to the patient.

Contact the patient by phone informing him or her that the questionnaire was not completed. Ask the patient if she is willing to complete one:

If yes, mail a blank questionnaire to the patient, and make arrangements for return of the questionnaire in a timely fashion. Record the date it was mailed and the date received on the questionnaire.

If this is not feasible, then ask the patient if she is willing to complete a questionnaire over the phone. If the patient agrees, read out questions 1-5 and range of possibilities, and record the answers. The visual analogue scale should not be completed in this case. Make a note on the questionnaire that the questionnaire was completed over the phone.

If no, note the reason why the questionnaire was not completed on the appropriate case report form.

- B. The patient goes on an extended vacation for several months and won't attend the clinic for regular visit(s).

Ensure that the patient has a supply of questionnaires, with instructions about when to complete them, and how to return them. If it is known beforehand, give the patient blank questionnaires at the last clinic visit; if the extended absence is not known in advance, mail the blank questionnaires to the patient. Written instructions may help ensure that the patient stays on schedule as much as possible.

- C. The patient does not want to complete the questionnaire in clinic.

Should the patient not wish to answer the questionnaire in the clinic but insists on taking it home, and failing to comply with the patient's wishes is likely to result in the questionnaire not being completed at all, then the patient may take the questionnaire home with instructions that it is to be completed the same day. When the questionnaire is returned, the date on which the questionnaire was completed should be noted and a comment made on the questionnaire as to why the patient took it away from the clinic before completion.

D. The patient is no longer attending clinic during the scheduled follow-up period.

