If these special arrangements are not possible or feasible, then the patient would not be required to complete the questionnaires, and this should be reported on the appropriate case report form.

Health Utilities Questionnaire – **ENGLISH**
CCTG Trial: CX.5

This page to be completed by the Clinical Research Associate

Patient Information

CCTG Patient Serial No: _____

Patient Initials: _____
(first-middle-last)

Institution: _____

Investigator: _____

Scheduled time to obtain quality of life assessment: please check (3)

Prior to randomization

At the time of first recurrence

After surgery prior to recurrence:

3 months

6 months

9 months

12 months

16 months

20 months

24 months

30 months

36 months

Other _____ (specify)

Were ALL questions answered? ___ Yes ___ No If no, reason: _____

Was assistance required? ___ Yes ___ No If yes, reason: _____

Where was questionnaire completed: home clinic another centre

Comments: _____

Date Completed: ____ - ____ - ____
 yyyy mmm dd

*PLEASE ENSURE THIS PAGE IS FOLDED BACK BEFORE HANDING
TO THE PATIENT FOR QUESTIONNAIRE COMPLETION.*

CCTG use only

Logged: _____
_____ - _____ - _____

Study Coord: _____
_____ - _____ - _____

Res Assoc: _____
_____ - _____ - _____

Data Ent'd: _____

Verif: _____

Health Utilities Index Mark 3 (HUI3) Questionnaire

CCTG: CX.5

This questionnaire contains a set of questions which ask about various aspects of your health. When answering these questions please think about your health and your ability to do things on a day-to-day basis, during the past week. For each question, please select one answer that best describes your level of ability or disability during the past week. Please answer all the questions yourself by circling the letter (a, b, c, ...) beside the answer that best applies to you. Choose the best single response that applies to you. There are no right or wrong answers; what we want is your opinion about your abilities and feelings. To define the past week period, please think about what the date was 7 days ago and recall the major events that you have experienced during this period. Please focus your answers on your abilities, disabilities and how you have felt during the past week.

You may feel that some of these questions do not apply to you, but it is important that we ask the same questions of everyone. Also, a few questions are similar; please excuse the apparent overlap and answer each question independently.

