17. How did you complete the questionnaire? Please select the one answer that best describes your situation.
- a. By myself, without any help from anyone else.
 - b. By myself, except someone else circled the answers on the questionnaire form for me.
 - c. With the help of someone else.
 - d. This questionnaire was completed by a family member, without help from the subject or patient.
 - e. This questionnaire was completed by a nurse or other health professional, without help from the subject or patient.
Please specify type of health professional: _____
 - f. This questionnaire was completed by another person, without help from the subject or patient.
Please specify relationship to subject or patient: _____

EQ-5D Questionnaire

CCTG: CX.5

By placing a tick in one box in each group below, please indicate which statements best describe your own health state today.

1. **Mobility**

- a. I have no problems in walking about
- b. I have some problems in walking about
- c. I am confined to bed

2. **Self-Care**

- a. I have no problems with self-care
- b. I have some problems washing or dressing myself
- c. I am unable to wash or dress myself

3. **Usual Activities** (*e.g. work, study, housework, family or leisure activities*)

- a. I have no problems with performing my usual activities
- b. I have some problems with performing my usual activities
- c. I am unable to perform my usual activities

4. **Pain/Discomfort**

- a. I have no pain or discomfort
- b. I have moderate pain or discomfort
- c. I have extreme pain or discomfort

[figure not shown]
5. **Anxiety/Depression**

- a. I am not anxious or depressed
- b. I am moderately anxious or depressed
- c. I am extremely anxious or depressed

To help people say how good or bad a health state is, we have drawn a scale (rather like a thermometer) on which the best state you can imagine is marked 100 and the worst state you can imagine is marked 0.

We would like you to indicate on this scale how good or bad your own health is today, in your opinion. Please do this by drawing a line from the box below to whichever point on the scale indicates how good or bad your health state is today.

**Your own
health state
today**

Please check to make sure you have answered all questions.

Please fill in your initials to indicate that you have completed this questionnaire: _____
Today's date (Year, Month, Day): _____

Thank you.

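### The telephone fallback for the Health Utilities Questionnaire covers only the EQ-5D items, so these calls never collect a complete HUI3

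*Protocol*

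**What the plan says.** The protocol collects utilities with a two-part booklet. Section 6.0 lists a "Health Economics questionnaire (composed of the HUI3 and EQ-5D"), and Section 9.1 and Appendix I describe it in the same way.

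In the booklet in Appendix VII, the first instrument is headed "Health Utilities Index Mark 3 (HUI3) Questionnaire". Its items run from 1 to 17, the last being "17. How did you complete the questionnaire". The EQ-5D follows, opening with "By placing a tick in one box in each group below, please indicate which statements best describe your own health state today". Its numbering restarts at 1 and ends at 5, and the visual analogue scale comes after item 5.

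Appendix VII, item 5, situation A applies when the form was not given out at the visit. Staff first telephone the patient and offer to mail a form. The telephone interview is the second step: "If this is not feasible, then ask the patient if she is willing to complete a questionnaire over the phone". The instruction for that call is "If the patient agrees, read out questions 1-5 and range of possibilities, and record the answers", followed by "The visual analogue scale should not be completed in this case". Staff then mark the form as completed by telephone.

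**The concern.** The wording fits a booklet that contains only the EQ-5D. The CX.5 booklet also contains the HUI3, and nothing in the situation A rule tells staff to read it out. A call made to rescue a missed assessment therefore leaves the HUI3 incomplete, although the form is marked as completed by telephone.

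Cost-utility is a secondary objective (Protocol Section 1.2). Section 2.7.3 names both the EQ-5D and the Health Utilities Index as possible sources of utility scores. What is at stake is the completeness of one of these two sources, in an appendix whose follow-up instructions aim to keep missing utility data to a minimum.

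There is also a smaller risk of misapplication. Two sets of items in the booklet are numbered 1 to 5, and the rule does not say which is meant.

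**Working it through.** No sample size, power or event figure is involved. The check counts items under each possible reading of the rule.

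**Inputs**
- HUI3: 17 numbered items (Appendix VII). Items 1–2 cover vision, 3–4 hearing and 5–6 speech. Items 7–15 cover mood, pain, walking, hand use, memory, thinking and basic activities. Item 16 is an overall health rating, and item 17 asks how the form was completed.
- EQ-5D: 5 items, each with three levels, plus the visual analogue scale (Appendix VII).
- The EQ-5D index is derived from the five-item descriptive system (Section 2.7.3). That section's count of 243 health states is reproduced by 3^5 = 243, so the scale is not needed for the index.

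**Items obtained under each reading**

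| Reading of the rule | EQ-5D items | HUI3 items | EQ-5D index | Complete HUI3 |
|---|---|---|---|---|
| EQ-5D items 1–5 | 5 of 5 | 0 of 17 | yes | no |
| Items 1–5 of both instruments | 5 of 5 | 5 of 17 | yes | no |
| First five items in the booklet (HUI3 1–5) | 0 of 5 | 5 of 17 | no | no |

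No reading gives a complete HUI3. The last two rows yield 5/17 = 29% of its items, or 5/15 = 33% if items 16 and 17 are set aside. Those five items are two on vision, two on hearing and one of the two on speech, so nothing is recorded on mood, pain, walking, hand use, memory, thinking or basic activities.

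The documents give no scoring or missing-item rule for the HUI3. The half-completed rule in SAP Section 7.8.1 covers the EORTC, FSFI and FSDS-R questionnaires only. Even if it were borrowed, 29% or 33% is below one half and the score would be missing.

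**Which reading is meant.** The sentence excluding the visual analogue scale decides this. Only the EQ-5D has such a scale, and it stands directly after EQ-5D item 5. The first row is the natural reading. The third would leave the sentence about the scale with no purpose.

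**Does it look deliberate?**
- The corresponding rule for the quality of life questionnaire (Appendix VI, item 5, situation A) has staff read the questions with no item limit. That booklet has 30 + 24 = 54 items. Reading the whole HUI3 and EQ-5D would take 17 + 5 = 22, so length does not explain the restriction.
- Appendix VII, item 8 has the HUI3 read aloud in clinic to patients physically unable to complete it, and allows for a telephone interview when such a patient is at home, with no limit to five items. Oral administration is therefore acceptable.
- No section says that the HUI3 is to be skipped by telephone.

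The restriction looks like wording carried over from a booklet with the EQ-5D alone. That is an inference; the documents do not say so.

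**The case against.** The strongest reply is that the rule does what it should: it secures the EQ-5D, a utility can be computed for each such call, and no document makes the HUI3 the source of the quality-adjusted life years. Section 2.7.3 offers the two instruments as alternatives and then describes only the EQ-5D. Section 14.7 names no instrument, and SAP Section 3.2 leaves the economic analysis plan for later. Much of this stands. It means that no harm to the cost-utility result can be shown, only that data on a scheduled instrument are not collected.

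The reply is also right about scope. The route is a second-line step within one situation. Situations B, C and D in the same item rely on supplied, take-home or mailed forms, and the appendix describes its instructions as a guide.

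A reader might go further and infer that, taken literally, the rule yields no EQ-5D either, because the HUI3 comes first in the booklet. The documents do not support this. The EQ-5D has its own items 1 to 5, and the exclusion of the visual analogue scale points to it. What remains is a risk that staff misread an unlabelled instruction.

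A reader might also infer that every telephone-completed HUI3 is lost. That is too broad, since the telephone interview in Appendix VII, item 8 carries no limit to five items.

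**Conclusion.** The point holds as a minor one. Calls made under Appendix VII, item 5, situation A, after mailing has proved not feasible, can give an EQ-5D index but never a complete HUI3. The rule can also be misapplied because it names no instrument.

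The size cannot be stated as a number of patients. Whatever share of scheduled assessments reaches this step, the same share lacks a complete HUI3. The documents give no figure for that share and no basis for assuming one. Only the secondary cost-utility endpoint is touched; the primary analysis is unaffected.

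The conclusion rests on the booklet as printed in Appendix VII and on staff following the instruction as written. That an HUI3 with whole areas of health unasked cannot be scored is an assumption, because the documents contain no HUI3 scoring rule.

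**What to change.** Replace the instruction in Appendix VII, item 5, situation A with: *read out all HUI3 questions and EQ-5D questions 1–5 with their response options; omit only the EQ-5D visual analogue scale.* This brings it into line with the telephone rule in Appendix VI. The cost is one sentence and slightly longer calls: 22 items in place of 5.

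The SAP puts the last enrolment at 29 November 2019 and the clinical cut-off at 29 November 2022, so new wording helps only assessments still to come. Section 9.1 continues the questionnaire annually until study closure.

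For forms already completed by telephone under this rule, the economic analysis plan should treat the HUI3 as missing and use the EQ-5D index where its five items were recorded. The telephone note that staff make on the form identifies these cases, and would also show any call where HUI3 items 1–5 were read by mistake. The same plan should say which utility instrument is primary. That costs a short rule in a document that the SAP says is still to be written.

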APPENDIX VIII - COVID-19 AND EMERGENCY SITUATIONS AND COMPLIANCE

Management of Protocol Variances in Emergency Situations

Compliance with the trial protocol should be ensured to every extent possible. However, specific variances from the protocol that occur as a result of efforts to minimize or eliminate hazards and protect the safety and well-being of patients are permissible in emergency situations.

In these rare circumstances, minor deviations that do not impact patient safety or willingness to participate or trial integrity, which have been justified and documented in the medical record by the QI/SI will not be considered to be REB reportable deficiencies requiring action, but must be reported to CCTG (e.g. in Electronic Data Capture (EDC) or using trial specific deviation logs as directed by CCTG) within 4 weeks of the end of the Emergency Situation, and to your REB at the next amendment or annual approval.

Centres should also discuss these reporting requirements with their local REB and review the trial website for additional guidance specific to the trial.

Minor Protocol Deviations:

- Missed or delayed protocol mandated visits or investigations on treatment or in follow up.
- Changes in study drug distribution (e.g. drug distributed remotely or IV drug given at satellite site), providing permitted by local SOPs, or written procedure established and is approved by CCTG or acceptable per further instruction from CCTG. Note there will be no exceptions for injectable/IV investigational agents as must be administered at participating site.
- Alternative methods for safety assessments (e.g. telephone contact, virtual visit, alternative location for assessment).
- Patient care and evaluations provided by non-research staff, providing overseen by QI/SI who must make all treatment decisions and ensure that all required information and results will be reported to allow central data submission. Includes physical exam, clinical laboratory tests, research blood collections that can be shipped centrally, imaging, non-investigational drug therapy*, standard radiation therapy, surgery, and other interventions that do not require protocol-specified credentialing*. *Must be approved by CCTG or acceptable per further instruction from CCTG.
- Re-treatment following extended treatment delays if protocol specifies that excessive delays require discontinuation, providing other protocol requirements for discontinuation have not been met and either discussed with CCTG or acceptable per further instruction from CCTG.

Note:

- Applicable only to COVID-19 and other CCTG designated emergency situations.
- No waivers will be given for eligibility, including performance of protocol mandated tests/imaging.
- Deficiencies will be issued if patients are enrolled when trial is on accrual hold, for unreported Serious Adverse Events as well as changes in drug distribution/administration and/or re-treatment after extended treatment delays when not discussed and approved by CCTG or acceptable per further instruction from CCTG.
- Deviations or changes that are believed to impact patient safety, compromise the study integrity or affect willingness to participate are still considered Major Protocol Violations and must be reported to CCTG and your REB. These include more than a minimal delay in protocol therapy administration.

2.1 Study Design

CX.5 is a multi-centre, international, prospective, randomized phase III trial of radical hysterectomy and pelvic node dissection versus simple hysterectomy and pelvic node dissection in patients with previously untreated, low-risk cervical cancer. The study is being conducted by the Canadian Cancer Trials Group.

This study opened to accrue patients on August 3, 2012 and the accrual to the study was closed on November 29, 2019 after required 750 patients were randomized.

The original statistical plan estimated that 49 pelvic relapses would have to be observed at the time of final analysis to demonstrate non-inferiority of a simple hysterectomy compared to a radical hysterectomy with pelvic relapse free survival being the primary end point. An interim analysis was planned at 25 events, which was predicted to be observed approximately at the end of accrual based on the assumptions in the original protocol. But only 14 pelvic recurrences were observed after 2 years of accrual completion. With the approval by the CCTG Data and Safety Monitoring Committee (DSMC), the protocol was amended in June of 2022 which changed the primary endpoint from pelvic relapse free survival to the pelvic recurrence rate at 3 years, since it is a timepoint of clinical interest and was used to derive the non-inferior limit for the hazard ratio of pelvic relapse free survival and sample size. The timing of final analysis was also changed to the time when the last recruited patients have been followed for three years. The planned interim analysis was also cancelled.

Since the last patient was enrolled on November 29, 2019, it was decided that November 29, 2022 will be the date of clinical data cut-off and the final analysis will be performed on a database which will be locked after all data observed before this clinical data cut-off date are received and cleaned. This analysis plan describes the analyses performed on this database.

The CCTG DSMC has been reviewing safety data annually and as otherwise required. These analyses have been prepared by a CCTG/Queen's Senior Biostatistician.

2.2 Treatment Allocation

A total of 700 patients would be enrolled. Eligible patients would be randomized in a 1:1 ratio to receive simple hysterectomy and pelvic node dissection or radical hysterectomy and pelvic node using the minimization method after stratified by cooperative group, intended use of SN mapping (yes vs. no), stage (IA2 vs. IB1), histological type (squamous vs. adenocarcinoma/adenosquamous), and tumour grade (1-2 vs. 3 vs. not assessable). A centralized system was used to randomize all patients in this study.

3. Objectives

3.1 Primary

The primary objective of this study is to evaluate whether treatment with simple hysterectomy and pelvic node dissection is non-inferior to treatment with radical hysterectomy and pelvic node dissection in terms of pelvic recurrence rate at 3 years.

3.2 Secondary

Secondary objectives are to compare the following endpoints between two treatment arms:

- Pelvic relapse free survival (PRFS)
- Extra-pelvic relapse free survival (EPRFS)
- Relapse free survival (RFS)
- Overall survival (OS)
- Rate of sentinel node detection
- Rate of parametrial involvement
- Rate of surgical margin involvement
- Rate of pelvic nodes involvement
- Treatment-related adverse events
- Patient report outcomes including quality of life and measures of sexual health
- Cost-effectiveness and cost-utility

Note: The analysis plan to address the last objective, i.e., evaluation of cost-effectiveness and cost-utility will be developed at a later date.

4. Endpoints

